## Recruitment and Remuneration

### Recruitment

**1 \* Describe plans for recruitment, including identification of potential participants, who is responsible for recruitment and how and when subjects will be recruited.**

Potentially eligible participants will be identified during visits to the Pediatric Gynecology program at BCH (including satellite sites) or the CIRS or MIGS programs at BWH. Patients will be identified by their clinical provider as potentially eligible.

If the patient is interested, the provider will contact the study team. An IRB-approved study brochure may be given to the patient, to allow her to contact the study team directly. A study coordinator or another member of the study team will meet with the patient to discuss options for involvement.

In some instances, providers may wish to give blanket approval for the study team to contact their patients, rather than referring individual patients. In these instances, the study team will contact patients through the mail or email with a recruitment letter (appendix L), and then follow up with the patient (by phone or email, if patient approved for research) one week later. This allows patients of very busy providers the opportunity to participate in the study. Patients are able to opt out of the follow up call/email by returning the opt out postcard (Appendix N) to the study team. Providers who give patient contact information to study staff will be only IRB-approved participants in the research.

We will also recruit by posting IRB-approved brochures in the waiting rooms of the clinics and other hospital areas and in local clinics. After a patient expresses interest in participating in the trial, a research assistant or another approved member of the study team will meet with the patient/family to discuss options for involvement and to sign the consent form. Prior to enrollment, patients will be asked what their highest endometriosis pain score has been within the last month. Only those patients with a score of 3/10 or greater will be eligible to enroll.

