## Privacy and Confidentiality

### Privacy

- 1 \* 'Privacy' refers to a person's desire to control access of others to themselves. Describe the steps that will be taken to protect and assure the privacy of the subject.**

**Detail specific actions the Research Team will take to ensure that privacy is protected through each phase of the study (e.g. access to medical records for recruitment, mailings to subjects, phone calls with subjects, research visits).**

Patients with endometriosis will be approached about the study in the gynecology clinic where they receive clinical care. In most cases, the treating physician will discuss participation in the study with the patient in a private office or treatment room, and will ask if they are willing to speak with the study coordinator. The physician will provide each patient with a study brochure for her review. Interested patients will meet with the study coordinator in a private setting to discuss involvement in the study. Patients will be made aware the study is voluntary and participation will not affect clinical care. For all participants, the consent process will take place in a private setting. Participants will be encouraged to ask questions and to illustrate full understanding of the study procedure and risks/benefits.

Other potential subjects may approach the study team in response to flyers posted in clinic, or given to them by their medical provider at the time of a clinic visit. Phone calls with potential subjects to screen for eligibility for participation will also be conducted in a private setting.

During research visits, participants will complete study questionnaires in a private room setting.

Participants will determine their preferred means of communication (phone call, email, text), and if there are any means of communication that they never wish to employ. When phone calls are made, the study will be referred to in general terms that will not disclose the exact nature of study participation. Information which may identify the purpose of the study or the disease status of the participant will not be recorded on voicemail or answering machine.

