**3 \* Describe provisions for minimizing risks to participants.**

Subjects are monitored closely throughout the course of participation by both the study team, and with their clinical care gynecology provider.

At the baseline study visit, we will measure blood samples for total cholesterol, HDL cholesterol, and triglyceride levels. This lipid profile will allow us to monitor for any individual changes in serum lipids from baseline, and for differences between treatment groups. In some studies of adult women, mildly deleterious effects on circulating lipid profiles have been seen in patients receiving treatment with norethindrone acetate (decreased HDL). Lipid profiles will be repeated at follow-up visits scheduled for 3 and 6 months after initiation of therapy. Blood samples will also be taken for liver function tests (AST, ALT) at each visit to allow us to monitor for any liver inflammation associated with the drug therapy. HbA1c will be taken at baseline and at 6 months to monitor for impairments in glucose metabolism. We will utilize a measurement of ESR and serum creatinine at each study visit to screen for the very unlikely development of a fibrotic disorder associated with low-dose cabergoline use. A physical examination will be performed at each visit to assess for acne, and cardiac auscultation will be done to assess for the presence of a cardiac murmur. The presence or absence of hormonal symptoms (mood changes, breast tenderness, acne, and changes in menstrual bleeding patterns) will be queried at each visit. The hormonal milieu will be assessed using serum measurements of estradiol and prolactin at baseline and each subsequent study visit. These laboratory studies will allow us to monitor cabergoline activity, and to determine compliance with cabergoline treatment in Group 2. If any cardiac murmur is identified during study participation, an echocardiogram will be performed.

Subjects will be discontinued from further study participation if any of the conditions that are listed as exclusion criteria for participation develop during the six months of active participation in the study. Because of the potential risk of adverse side effects, patients in the treatment trial will be monitored closely during the 6-month study period with laboratory assessments and physical examinations every three months.

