## Blood Collections

**1 Select the method(s) of blood collection.**

- 1.1  Venipuncture
- 1.1.1  At time of clinically indicated procedure
- 1.1.2  At time specifically for research
- 1.2  Heel/finger/ear sticks
- 1.3  From catheter or heparin lock
- 1.4  Other

*If Other:*

1.4.1 Please specify.

2 \* **How many individual samples will collected (not number of sticks)?**

One sample will be collected per research study visit, for a total of 3 samples over 6 months.

*Note: Multiple withdrawals of blood from an indwelling venous line are to be considered more than one collection.*

3 \* **What is the period of time the samples will be collected (please specify in weeks or if less than weeks in days)?**

Samples will be collected at baseline, 3 months, and 6 months.

4 \* **Specify the total amount of blood collected in mls.**

maximum 40mLs

5 \* **Will research subjects be less than 16.5 kg?**

Yes  No

*If YES:*

5.1 **Will the total amount of blood to be drawn from children less than 16.5 kg be more than 3mL/kg?**

Yes  No

**Title: Novel Treatments for Endometriosis (NOTE): Dopamine Receptor Agonist Therapy for Pain Relief in Women Suffering from Endometriosis Pilot Study**

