### Statistical Plan

The **primary test of interest** for the trial is a comparison of the mean change in pain score, as measured by the BPI, between groups over time. A linear mixed-effects model will be used to estimate the change over time within each group; the model will include fixed effects for group, time, and the group by time interaction and random effects for subject and time (to account for the correlation among observations from the same subject). Estimates and 95% confidence intervals for group differences at each time point will be created using linear contrasts. This pilot study is not designed to determine statistical superiority or equivalence of norethindrone acetate versus cabergoline; rather, the estimates obtained from the mixed model will be used to plan a future randomized controlled trial. **Secondary endpoints** will be analyzed similarly.

**Sample Size:** As the proposed investigation is a pilot study, the sample size has been chosen to provide estimates for the change over time in each group while minimizing the number of subjects exposed to the study treatments. Assuming that we will have an 80% trial completion rate, we will recruit 7 patients to each arm in order to have 5 completers in each randomization group.

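### The SAP's between-group intervals can be read as unadjusted BPI levels at each visit rather than changes, and the model makes no use of baseline BPI to adjust the comparison

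*SAP*

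**What the plan says.** The SAP, Statistical Plan, calls the primary test "a comparison of the mean change in pain score, as measured by the BPI, between groups over time". On the model it says that "the model will include fixed effects for group, time, and the group by time interaction and random effects for subject and time". On the between-group output it says: "Estimates and 95% confidence intervals for group differences at each time point will be created using linear contrasts". Secondary endpoints are to be handled in the same way. The SAP adds that the pilot is not meant to establish superiority or equivalence and that its estimates will feed the planning of a later trial.

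The SAP does not list the visits that enter the model, or say whether time is categorical or linear. The protocol implies a baseline BPI without stating one:

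- Privacy and Confidentiality: "During research visits, participants will complete study questionnaires in a private room setting".
- Risks and Benefits, question 3, on lipid profiles: "follow-up visits scheduled for 3 and 6 months after initiation of therapy".
- Blood Collections: "Samples will be collected at baseline, 3 months, and 6 months".
- Protocol and Appendices lists the BPI short form among the instruments. It also lists a separate protocol file, which was not available for this review and may give the schedule.

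**The concern.** Two things are left open. First, the primary sentence is about change, but the sentence that promises intervals is about differences at each visit and does not name the scale. Read literally, it yields raw level differences, one of them at baseline, where no treatment effect exists to estimate.

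Second, whichever scale is meant, baseline is not used to adjust. If it enters the model as a response with a separate mean in each arm, the level contrast ignores the chance baseline difference and the change contrast subtracts all of it. Neither is the efficient use of a correlated baseline. With 5 completers per arm, chance imbalance is often large. The estimates are the pilot's only product, so it is worth defining them once, in advance, by the method with the smaller error.

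**Working it through.** **The plan's own figure.** 5 completers at 80% completion needs 5/0.8 = 6.25, rounded up to 7 per arm. This agrees with the SAP and is not affected by what follows.

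**Inputs.** n = 5 completers or 7 recruited per arm (SAP, sample size). Visits at baseline, 3 and 6 months (protocol, as quoted above). The documents give neither the BPI SD nor the correlation rho between visits, so results are in SD units and rho is assumed over 0.2 to 0.9. Time is taken as categorical and data as complete.

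**What each contrast returns.** With group, time and group by time, the level difference at a visit is the group term plus the interaction, and the change difference is the interaction alone. They differ by the observed baseline difference. In one simulated data set the change contrast was 0.354 and the baseline difference 0.219, so the level contrast was 0.354 + 0.219 = 0.573.

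**Size of chance imbalance.** The baseline difference has SD sqrt(2/n): 0.63 for n = 5 and 0.53 for n = 7. It exceeds 0.5 SD in 43% and 35% of trials. For n = 5 its mean size in those trials is 0.860 SD. At rho 0.5 it moves the level contrast by 0.5 × 0.860 = +0.43 SD and the change contrast by (0.5 − 1) × 0.860 = −0.43 SD. The adjusted contrast moves by 0.00 to 0.03 SD.

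**Standard errors with the covariance known.**
- Level: sqrt(2/n)
- Unadjusted change: sqrt(2/n) × sqrt(2(1 − rho))
- Common baseline mean: sqrt(2/n) × sqrt(1 − rho²)

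| rho (n = 5) | Level | Change | Common baseline |
|---|---|---|---|
| 0.3 | 0.632 | 0.748 | 0.603 |
| 0.5 | 0.632 | 0.632 | 0.548 |
| 0.7 | 0.632 | 0.490 | 0.452 |
| 0.8 | 0.632 | 0.400 | 0.379 |

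**With the covariance estimated.** In complete-data simulation with a random-intercept covariance, the common-baseline contrast at month 6 had root mean squared error below both alternatives at every rho from 0.2 to 0.9. At rho 0.5 it was 0.56 against 0.63 and 0.63 SD (n = 5), and 0.47 against 0.54 and 0.54 SD (n = 7). That is 1 − 0.56/0.63 = 11% and 1 − 0.47/0.54 = 13% lower.

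**Where the gain vanishes.** Even with known covariance, the ratio to level is sqrt(1 − 0.2²) = 0.98 at rho 0.2, and the ratio to change is sqrt((1 + 0.9)/2) = 0.97 at rho 0.9. Estimating the covariance takes back part of these small gains.

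**If a baseline slope is estimated freely instead.** With t intervals and n = 5, the width relative to level is (2.365/2.306) × sqrt(1 + 1/6) × sqrt(1 − rho²) = 1.108 × sqrt(1 − rho²). Relative to change it is 1.108 × sqrt((1 + rho)/2). That interval is wider than level when rho is below 0.43 (by up to 11% near 0). It is wider than change when rho is above 0.63 (8% at 0.9, approaching 11% near 1).

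**The case against.** The strongest reply is that the estimand is already fixed in context. The SAP speaks of change in the primary comparison, in the purpose of the model and in the sample-size rationale, and the group-by-time interaction delivers the between-group change. This stands as far as it goes: the text is ambiguous about its reported intervals and does not contradict itself. If naming the contrast, the visits or the form of time were all that was missing, it would be a matter of detail.

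A second reply is that baseline adjustment is a preference, since it can widen the interval at some correlations. That holds for a freely estimated slope with t intervals at n = 5, as shown above. It does not hold for the common-mean model in the setting simulated, where error was no larger than either alternative across the assumed range.

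A third reply is that the gain depends on the covariance model. This stands. The simulations did not fit the SAP's random effects for subject and time, and did not use partial data from non-completers. The entry rule ("Only those patients with a score of 3/10 or greater will be eligible to enroll") could also compress baseline variance. If baseline SD were 0.8 of follow-up SD (assumed), an equal-variance random-intercept model would leave an average shift of 0.12 SD in imbalanced trials at n = 5 and rho 0.5, against 0.00 with an estimated slope.

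A reader might go further and infer that the choice of contrast could decide which drug looks better, because level and change have opposite signs in 33% of null trials at rho 0.5. The documents do not support that reading. These are noise-level estimates: with n = 5, signs differ while either 95% interval excludes zero in only about 1% of such trials. The SAP also disclaims any superiority or equivalence conclusion.

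**Conclusion.** The point holds as a minor one. The reported between-group intervals are open to a level reading that does not match the stated comparison of change, and the model leaves baseline BPI unused for adjustment. At rho 0.5 the available improvement is roughly a tenth of the root mean squared error (0.63 to 0.56 SD at n = 5; 0.54 to 0.47 SD at n = 7). It shrinks towards nothing against level at low rho and against change at high rho.

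This rests on an assumed rho and SD scale, complete data, a random-intercept covariance, categorical time, and a baseline BPI that the visit schedule implies but the supplied text does not state. It would be wrong to infer bias: every candidate contrast is unbiased over randomisation. No test, power figure or decision rule is affected, because the pilot has none.

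**What to change.** Confirm that the BPI is collected at baseline, and add about two sentences to the Statistical Plan, for example:

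> BPI at baseline, month 3 and month 6 will be modelled as responses with time categorical, and the two arms will share one baseline mean. The between-group differences in change from baseline at months 3 and 6 will be reported with 95% confidence intervals.

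These replace the unadjusted visit differences and drop any baseline group contrast. Apply the same rule to secondary endpoints that have a baseline, and state the covariance structure, since the adjustment depends on it. If the common mean is not adopted, the minimum is to say that the contrasts are differences in change.

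The cost is the wording and reliance on the modelled covariance. No new data or patients are needed, and within-arm changes still come from the same model. Estimating a baseline slope freely instead would risk an interval up to about 11% wider at n = 5, as shown above.
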